5.1.2 Secondary Study Endpoints

Additional outcomes will include physiological and psychological domains relevant to AUD including self-reported craving, depression, and anxiety; responses to personalized scripts designed to elicit stress- and cue-induced craving and anxiety; and drinking outcomes across 8 weeks of treatment and 4 weeks of follow-up.

CONFIDENTIAL

This material is the property of the NYU School of Medicine and Langone Health
Do not disclose or use except as authorized in writing by the study sponsor

AUD-Related Measures:

The Penn Alcohol Craving Scale (PACS) [105] will be used to assess craving. This scale has 5 Likert-scaled items with excellent internal consistency and evidence of predictive, construct, and discriminant validity. Mood and Anxiety will be measured with the Beck Anxiety Inventory (BAI) [106] and Beck Depression Inventory-II (BDI-II) [107] scales before CBD treatment, at the end of treatment, and at the 2 week follow-up. Self-efficacy will be assessed using the Alcohol Abstinence Self-Efficacy Scale (AASE) [108], a self-report questionnaire which has been used widely in the alcohol treatment research, both as a predictor of outcome and as a patient-treatment matching variable [109, 110].

The Cue and Stress Response Task will be performed at the 5- week time-point using methodology developed in [name]'s lab, similar to those in used in past studies with alcohol dependent patients [112, 113]. [name] will provide consultation on the implementation of these methods. Briefly, imagery scripts will be developed at baseline and again following 4 weeks of treatment. Stress imagery scripts will be based on a recent highly stressful situation the participant has experienced unrelated to alcohol use. Alcohol cue scripts will be derived from a recent event that included alcohol-related stimuli and led to alcohol use. Neutral or relaxing scripts will also be developed. All scripts will be developed by obtaining specific details of stimulus and response, including contextual details, cognitive and verbal content, affective experience, and bodily sensations. These details form the basis of a 5-minute imagery script, which will be developed for each of the three conditions. Imagery sessions will be structured with a 5-minute pre-imagery period, a 5-minute imagery period, and a 5-minute recovery period. Pulse, skin conductance, heart rate variability, and blood pressure will be monitored during each imagery session with an ADInstruments PowerLab 4/30 Galvanic Skin Response device and a Contec Patient Monitor. In Human laboratory studies with CBD, skin conductance and amygdala activation were reduced by CBD in a closely correlated manner [59], suggesting threat-related sympathetic arousal may serve as a proxy for amygdala activation [114]. Participants will complete Likert scale ratings of vividness, craving, anxiety, and the 30-item Differential Emotion Scale [112, 113] following each of the three periods. After each condition, a progressive relaxation procedure will be implemented to facilitate return to baseline of vital signs, craving and anxiety, an approximate period of 10 minutes, as shown in previous research from the [name] lab [112, 113]. The entire imagery protocol will take 120 minutes. The order of the sessions will be randomized and counterbalanced among participants. This task will be completed at 5 weeks, i.e. after 1 week of treatment at 1200mg daily. At this point, we expect steady-state circulating CBD levels to have been reached. It is important to assess stress- and cue- response at the high dose because it is possible that anxiolytic effects decrease at high doses of CBD, while effects on alcohol consumption are expected to increase with dose.

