Alcohol Abstinence Self-efficacy "P"		✓				✓					
Short Inventory Of Problems "P"		✓				✓					
Penn Alcohol Craving Scale "P"		✓				✓					
Self-compassion Short Form "P"		✓				✓					
Beck Anxiety Inventory		✓				✓					
Beck Depression Inventory		✓				✓					
C-SSRS		✓				✓					
PTSD-Related Domains											
THQ		✓									
CTQ		✓									
PCL-5											
Cue/Stress Script Interview											
Imagery Scripts			✓								
Cue/Stress Task								✓			

CONFIDENTIAL

This material is the property of the NYU School of Medicine and Langone Health
Do not disclose or use except as authorized in writing by the study sponsor

Script Randomization					✓			
Alcohol Script Pre-Imagery *Pt					✓			
Alcohol Script Imagery *Pt					✓			
Alcohol Script Recovery *Pt					✓			
Neutral Script Pre-Imagery *Pt					✓			
Neutral Script Imagery *Pt					✓			
Neutral Script Recovery *Pt					✓			
Stress Script Pre-Imagery *Pt					✓			
Stress Script Imagery *Pt					✓			
Stress Script Recovery *Pt					✓			
Differential Emotions Scale IV *Pt					✓			
Physiological Stress Response Results					✓			
Alcohol Use								*
Follow Up Timeline Followback		✓		✓	✓	✓	✓	✓
Medication/Clerical								**
Research Visit Form	✓	✓	✓		✓	✓	✓	✓
Menstrual Calendar	✓	✓	✓		✓	✓	✓	
Medication Dispensing	✓		✓		✓	✓	✓	
Medication Compliance *Pt*			✓		✓	✓	✓	
Medication Management	✓		✓		✓	✓	✓	
Participant Treatment Assignment Guess *Pt*							✓	
Study Medication Questionnaire *Pt*							✓	
Treatment Satisfaction *Pt*							✓	
Unscheduled Forms								
Study Termination Form								
Consent Withdrawal								
Contact Attempts								

* should we do a separate phone form?
** medication management session documentation? Or just a question in dispensing form

8 Study Procedures and Schedule

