The Cue and Stress Response Task will be performed at the 5- week time-point using methodology developed in [name]'s lab, similar to those in used in past studies with alcohol dependent patients [112, 113]. [name] will provide consultation on the implementation of these methods. Briefly, imagery scripts will be developed at baseline and again following 4 weeks of treatment. Stress imagery scripts will be based on a recent highly stressful situation the participant has experienced unrelated to alcohol use. Alcohol cue scripts will be derived from a recent event that included alcohol-related stimuli and led to alcohol use. Neutral or relaxing scripts will also be developed. All scripts will be developed by obtaining specific details of stimulus and response, including contextual details, cognitive and verbal content, affective experience, and bodily sensations. These details form the basis of a 5-minute imagery script, which will be developed for each of the three conditions. Imagery sessions will be structured with a 5-minute pre-imagery period, a 5-minute imagery period, and a 5-minute recovery period. Pulse, skin conductance, heart rate variability, and blood pressure will be monitored during each imagery session with an ADInstruments PowerLab 4/30 Galvanic Skin Response device and a Contec Patient Monitor. In Human laboratory studies with CBD, skin conductance and amygdala activation were reduced by CBD in a closely correlated manner [59], suggesting threat-related sympathetic arousal may serve as a proxy for amygdala activation [114]. Participants will complete Likert scale ratings of vividness, craving, anxiety, and the 30-item Differential Emotion Scale [112, 113] following each of the three periods. After each condition, a progressive relaxation procedure will be implemented to facilitate return to baseline of vital signs, craving and anxiety, an approximate period of 10 minutes, as shown in previous research from the [name] lab [112, 113]. The entire imagery protocol will take 120 minutes. The order of the sessions will be randomized and counterbalanced among participants. This task will be completed at 5 weeks, i.e. after 1 week of treatment at 1200mg daily. At this point, we expect steady-state circulating CBD levels to have been reached. It is important to assess stress- and cue- response at the high dose because it is possible that anxiolytic effects decrease at high doses of CBD, while effects on alcohol consumption are expected to increase with dose.

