21.2 Statistical Hypotheses

Hypothesis 1a: Within-group circulating CBD levels will stabilize within one week, i.e. pre-CBD dosing (12 hour) levels obtained after 1 week of treatment will not differ from those obtained after 4 weeks of treatment at each dose.

Hypothesis 1b: Circulating CBD levels obtained at the 1200 mg/day dose will be comparable to those associated with anti-additive effects in animal models, i.e., in the range of 200-400 ng/ml.

Hypothesis 1c: No clinically significant cognitive or motoric impairments, CBD-related serious adverse events, or persisting adverse effects will be observed.

Hypothesis 2a: Relative to placebo, CBD will improve self-report measures of craving, anxiety, mood, and self-efficacy.

Hypothesis 2b: Relative to placebo, CBD will be associated with decreased stress- and alcohol cue-induced craving and physiological stress response

Hypothesis E: Relative to the placebo-treated group, CBD-treated participants will have fewer heavy drinking days during and for four weeks after treatment with 1200mg/day CBD vs. placebo.

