21.3.3 Analysis of the Secondary Endpoint(s)

For Hypothesis 2a, between- and within- group differences on measures of craving, anxiety, depression, and self-efficacy (T1, T3, T4, T6, T7, T8) will be evaluated. For Hypothesis 2b, linear mixed effects models will be constructed as described by [name] et al. [123] with treatment group (CBD vs. placebo) included as a fixed

CONFIDENTIAL

This material is the property of the NYU School of Medicine and Langone Health
Do not disclose or use except as authorized in writing by the study sponsor

between-subjects factor, time (nested factor including pre-imagery, imagery, and recovery periods at both T3 and T6) and script type (stress, alcohol cue, neutral) as fixed within-subjects factors, with subject as a random effect. Between- and within- group comparisons and interactions for measures of craving, anxiety, and physiological stress response will be assessed.

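### Imagery scripts are written again after 4 weeks of blinded treatment and the plan does not say which set is used at T6, so a lower response on CBD may not show lower reactivity to a comparable cue

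*Combined protocol and SAP*

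**What the plan says.** Sections 5.1.2 and 8.1 describe the task in the same words.

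- **Timing of the scripts:** "Briefly, imagery scripts will be developed at baseline and again following 4 weeks of treatment".
- **Source event for the stress script:** the plan asks for a recent, highly stressful experience that had nothing to do with drinking.
- **Source event for the alcohol script:** "Alcohol cue scripts will be derived from a recent event that included alcohol-related stimuli and led to alcohol use". A neutral or relaxing script is also made.
- **Content:** "All scripts will be developed by obtaining specific details of stimulus and response, including contextual details, cognitive and verbal content, affective experience, and bodily sensations".
- **Timing of the task:** "This task will be completed at 5 weeks, i.e. after 1 week of treatment at 1200mg daily".

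Hypothesis 2b in 21.2 reads: "Relative to placebo, CBD will be associated with decreased stress- and alcohol cue-induced craving and physiological stress response". The model for it in 21.3.3 uses a different timing of the task: "time (nested factor including pre-imagery, imagery, and recovery periods at both T3 and T6".

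The documents do not say which script set is played at T6. They give no method for rating or matching script intensity and no rule for a participant with no recent drinking event. The baseline covariates in 21.3.1 do not cover script content. Vividness is rated after each period, but no use of the rating is stated.

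**The concern.** A script written at week 4 from a recent event can draw on what happened, or how it was felt, while the participant was taking CBD or placebo. Because the script also records the participant's own reaction, a treatment effect on anxiety or craving can enter the stimulus itself. Randomisation balances pre-dose scripts between arms in expectation. It does not balance material that treatment can change, and blinding does not close that path.

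The alcohol script has a further difficulty. At baseline a recent drinking event is close to assured, because 6.1 requires six or more heavy drinking days within the 30 days before screening. By week 4 it is not assured. Participants enter wanting to drink less or stop (6.1), and all of them receive Medical Management (7.3). Someone who has stopped would have an older alcohol script or none, so the availability of the stimulus would depend on an outcome.

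At stake is the reading of Hypothesis 2b. A smaller response on CBD could mean less reactivity, or a milder script, and the planned analysis cannot separate the two.

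**Working it through.** **1. Which session could week-4 scripts serve?** Sections 5.1.2 and 8.1 place the task at T6 only. Section 21.3.3 models T3 (week 1) and T6 (week 5). Only T6 falls after week 4, so on either reading T6 is the only session at which week-4 scripts could be used. This is an inference, since no sentence says so. If T3 used baseline scripts and T6 used week-4 scripts, the T3-T6 contrast would also mix script set with dose and time on treatment.

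**2. Can treatment reach those scripts?** Hypothesis 2a predicts better self-rated craving, anxiety, mood and self-efficacy on CBD. Section 21.3.3 assesses these at T3 and T4, among other visits, so the plan itself looks for such effects in weeks 1-4.

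**3. What do the schedule and visit lists add?** The row "Imagery Scripts" in the schedule table appears to carry one tick, at baseline. The table text is not reliable on this. It shows single ticks for CDT and LFT collection, although 8.2 requires CDT at baseline, 4 and 8 weeks, and 5.1.1 requires LFTs at screening and weeks 4, 8 and 9. The visit lists in 8.3.2 and 8.3.3 mention script development at neither T1 nor T4, and list the task at T6 but not T3.

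**4. The plan's own figure.** Section 21.4 gives d = 0.3 for Hypothesis 2b at power 0.95, alpha 0.05 and 40 participants in two groups.

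- As a plain comparison of 20 against 20 it does not reproduce: exact t power at 0.3 is 15.2% two-sided, and the effect detectable at 95% power is 1.17.
- As a group-by-measure interaction with an assumed within-subject correlation of 0.5, 18 measures (3 periods x 3 scripts x 2 sessions) give a detectable d of 0.287 and power of 96.8% at 0.3. Nine measures (T6 only) give 0.36 and 82.4%.

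The basis of d = 0.3 is a separate matter. It bears on this point only because the number of sessions may enter it.

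**5. Illustration of size (assumptions, not document figures).** Suppose there is no true effect on reactivity, but script content shifts the arm difference by b SD. With 20 per arm (40 randomised 1:1), the noncentrality is b x sqrt(20 x 20 / 40) = 3.162b on 38 df. The rejection rate of a two-sided 5% t-test is:

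| b (SD) | noncentrality | rejection rate |
|---|---|---|
| 0.1 | 0.316 | 6.1% |
| 0.2 | 0.632 | 9.5% |
| 0.3 | 0.949 | 15.2% |
| 0.5 | 1.581 | 33.8% |

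One way to reach such values of b is (between-arm gap in script intensity) x (correlation of intensity with response). With an assumed correlation of 0.3 to 0.5:

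- A gap of 0.2 SD, the size 21.4 names as detectable for 2a, gives 0.2 x 0.3 = 0.06 to 0.2 x 0.5 = 0.10.
- A gap of 0.5 to 1.0 SD gives 0.5 x 0.3 = 0.15 to 1.0 x 0.5 = 0.50.

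The upper end therefore needs an intensity gap well above 0.2 SD.

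**The case against.** The strongest reply is that the defect is inferred. Nothing says the week-4 set replaces the baseline set, the word *recent* is undefined and could reach back before treatment, and the alcohol script needs only some drinking, not heavy drinking. A participant without any event would have to be abstinent for the whole of whatever *recent* covers. All of this stands, and it is why the point is conditional. It does not explain why a second set is written, or stop that set being used.

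A second reply is that the randomised comparison remains valid. That also stands: the arm difference at T6 estimates a total effect of treatment, including any effect through script content. But Hypothesis 2b is framed around induced responses, and 5.1.2 offers sympathetic arousal as a possible proxy for amygdala activation. That reading needs comparable cues.

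A reader might infer that the trial predicts less heavy drinking in weeks 1-4, which would strengthen the alcohol-script argument. The stated prediction (4.2; Hypothesis E in 21.2) covers the 1200 mg period and the four weeks after it. The analysis in 21.3.10 runs from T1, but that is not a prediction for weeks 1-4. The argument here rests on Hypothesis 2a.

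A reader might also take the single schedule tick as proof that scripts are made only at baseline. The table text is too damaged to carry that weight.

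**Conclusion.** The concern holds in conditional form. The plan provides for scripts that treatment can influence, places them where T6 is their only evident use, and describes no matching, adjustment or missing-event rule. If they are used, a lower response on CBD may not show reduced reactivity to a comparable cue.

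The stronger statement, that Hypothesis 2b is biased or that CBD participants will bring milder scripts, is not supported: the documents give no script-intensity data and do not fix the direction. The 6% to 34% range illustrates assumed shifts of 0.1 to 0.5 SD in a simple t-test. It is not an estimate for the planned mixed model. For a secondary endpoint in a 40-participant proof-of-concept trial, the change should be made, with medium confidence in the concern.

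**What to change.** 1. In 5.1.2 and 8.1, state that the T6 task uses the stress, alcohol and neutral scripts developed at T1 before the first dose, and delete the clause on developing them again after 4 weeks.
2. In the same edit, reconcile 5.1.2 and 8.1 (task at T6) with 21.3.3 (T3 and T6), the schedule table and the visit lists in 8.3.2 and 8.3.3. If a T3 session is kept, draw the scripts for both sessions from T1.
3. If week-4 scripts have already been used, record which set each participant received and add a sensitivity analysis restricted to participants tested with pre-dose scripts.
4. Report vividness ratings by arm.

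The cost is protocol wording, and one script-development session is saved. The downside is that scripts are recorded 5 weeks before use instead of 1 (5 - 4 = 1) and may be less vivid. The delay is the same in both arms, and the vividness ratings already collected will show any loss. If T3 is kept, replaying the same scripts at T6 may bring habituation, which should be weighed when deciding on that session.

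### Hypothesis 2b model leaves out the randomized script position, which costs precision on the stress and cue contrasts but does not bias them

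*Combined protocol and SAP*

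**What the plan says.** Sections 5.1.2 and 8.1 describe one 120-minute imagery protocol. It uses a 5-minute script, "which will be developed for each of the three conditions", with a pre-imagery, an imagery and a recovery period for each. About 10 minutes of progressive relaxation follow each condition. On sequence, the protocol says: "The order of the sessions will be randomized and counterbalanced among participants". The schedule table after section 7.3.2 lists "Script Randomization" as an item, so the assigned order should be available for analysis.

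Section 21.3.3 specifies the Hypothesis 2b model as a linear mixed model "with treatment group (CBD vs. placebo) included as a fixed" between-subjects factor. The remaining terms are period and "script type (stress, alcohol cue, neutral) as fixed within-subjects factors, with subject as a random effect". The target is stated as: "Between- and within- group comparisons and interactions for measures of craving, anxiety, and physiological stress response will be assessed". There is no order, position or sequence term. Section 21.3.1 adds baseline covariates, but nothing on order. Nowhere is it said that orders are balanced within treatment arm. Section 21.1 promises a formal SAP before database lock and unblinding.

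**The concern.** Counterbalancing an order and inserting a relaxation step both treat position as something that may matter, through habituation, fatigue or residual arousal. A design factor of this kind normally belongs in the model. If it is left out, its variance goes into the residual. Because balance within arm is not promised, the arms can also differ by chance in which script came early.

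Hypothesis 2b is about stress- and cue-induced response, so its contrasts compare scripts within a person and then between arms. Those are the contrasts that position reaches. With 20 participants per arm, precision on them is scarce.

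**Working it through.** **The plan's own figure.** Section 21.4 gives a detectable effect of d = 0.3 for Hypothesis 2b at power 0.95, N = 40, alpha = 0.05. A plain two-sample comparison with 20 per arm detects d = 1.17 at that power. A group-by-within interaction at an assumed correlation of 0.5 detects 0.36 with 9 measures (3 periods × 3 scripts) and 0.287 with 18 (the same at T3 and T6). If the figure is Cohen's f, f = 0.3 with 2 measures has 95.9% power. The basis is not stated, so 0.3 can be neither confirmed nor refuted, and it is not used as a yardstick below.

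**Inputs.** From the documents: 40 participants, 1:1, so 20 per arm; three scripts. Inferred: 3! = 6 orders. Assumed: a linear position effect of b SD per step and a within-person correlation ρ of 0.5 or 0.7.

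**Step 1, arm effect averaged over scripts.** Every participant fills positions 1, 2 and 3, so everyone's mean position is 2. With complete data the arm difference in mean position is exactly 0 and an additive effect cancels.

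**Step 2, one script.** Position is uniform on 1, 2, 3, with variance 2/3. The SD of the arm difference in mean position is √(2/3 × 2/20) = 0.26 steps. At b = 0.3 this is a chance shift of 0.3 × 0.26 = 0.08 SD, centred on zero, against a standard error of √(2/20) = 0.32 SD.

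**Step 3, script minus neutral, by arm.** Over the six orders the position difference is ±1 in four and ±2 in two, so its variance is (4×1 + 2×4)/6 = 2. The SD of the arm imbalance is √(2 × 2/20) = 0.45 steps; simulation with orders balanced overall but not by arm also gives 0.45. Balancing within arm gives 0.13. In the overall-balanced case the arms differ by 4 or more in the number hearing the stress script first in 23 to 24% of trials.

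**Step 4, cost to the contrast.** Without position, the variance of a within-person script difference is 2(1−ρ) + 2b² rather than 2(1−ρ). The standard error inflates by √[(2(1−ρ) + 2b²) / 2(1−ρ)]. At ρ = 0.5 and b = 0.3 this is √(1.18/1) = 1.086. Power for a test with 80% when position is modelled becomes Φ(2.80/1.086 − 1.96) = 73.2%.

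| b (SD per step) | SE inflation, ρ = 0.5 | Power, from 80% / 95% | SE inflation, ρ = 0.7 | Power, from 80% / 95% |
|---|---|---|---|---|
| 0.1 | 1.0% | 79.2 / 94.6% | 1.7% | 78.7 / 94.4% |
| 0.2 | 3.9% | 76.9 / 93.4% | 6.5% | 74.9 / 92.3% |
| 0.3 | 8.6% | 73.2 / 91.3% | 14.0% | 69.0 / 88.5% |
| 0.5 | 22.5% | 62.8 / 83.7% | 35.4% | 54.3 / 75.9% |

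The chance imbalance in Step 3 and the inflation here are the same loss seen two ways; they should not be added.

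**Step 5, simulation of the split-plot analysis** (2,000 runs per setting, effect 0.9 SD on one script). At b = 0.2, 0.3 and 0.5, power without position was 76%, 72% and 62%; with position it was 78%, 78% and 81%. Type I error at b = 0 to 0.5 was 4.6 to 6.1% without position and 4.5 to 5.4% with it.

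**Step 6, induced response (arm × script × period).** A position shift that is constant across periods cancels from imagery minus pre-imagery. It does not cancel from the residual of a model whose only random effect is subject. In simulation, power near 80% fell to about 79% at 0.25 SD per step and 67% at 0.5 without position, and stayed at 80 to 82% with it.

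**The case against.** **Size is assumed.** No document gives a position effect, and the relaxation step exists to return craving, anxiety and vital signs to baseline. At 0.1 SD per step the loss is about 1 point of power. An effect of 0.5 per step means a full SD of drift over three scripts, for which there is no evidence. This stands, and is why a range is shown.

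**The induced contrast is partly protected.** A constant shift cancels from the imagery-minus-pre-imagery estimate. True of the estimate, but Step 6 shows that the test still loses power through the residual. It is also true that a position main effect would not remove a position effect that differs by period, such as waning reactivity.

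**The model text may be incomplete.** Section 21.3.3 follows a cited publication that cannot be checked here, and a formal SAP is still to come. Either might include order. That is a reason to write the term down now.

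**Stronger readings that do not hold.** A reader might infer that order confounds the CBD–placebo comparison. It does not: order is randomized, the imbalance averages zero, type I error stays near nominal, and the arm effect averaged over scripts is untouched. A reader might also blame the fact that 20 does not divide by six. That is minor: the number of orders is inferred, and balancing within arm would leave an imbalance SD of only 0.13 steps. The protocol's wording is silent on within-arm balance and does not exclude it.

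**Conclusion.** The omission is clear from the text: a randomized and apparently recorded factor is missing from the Hypothesis 2b model. The consequence is lost precision on script-specific and arm-by-script contrasts, without bias. Under ρ = 0.5 and a linear, additive position effect the loss is negligible at 0.1 SD per step, about 3 points from 80% power at 0.2, 7 at 0.3 and 17 at 0.5; it is larger at ρ = 0.7. These sizes rest on assumptions that the documents neither support nor rule out. For a secondary hypothesis in a 40-person proof-of-concept trial this is a low-cost improvement and not a threat to the trial's validity.

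**What to change.** In section 21.3.3, or in the formal SAP before unblinding, add script position (1, 2, 3) as a fixed within-subject factor in the Hypothesis 2b model, using the order from the script randomization form. If reactivity is expected to change with position, state in advance whether a position-by-period term is also fitted (2 × 2 = 4 further degrees of freedom).

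If the order list can still be changed, balance the script orders within treatment arm. Balance alone is not enough, because unmodelled position variance would still sit in the residual.

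Cost: a sentence of SAP text, two model degrees of freedom, no new data, and about 1 point of power if order has no effect (79% to 78% in one simulation; 81.7% to 80.0% in that of Step 5).

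While editing, reconcile a separate discrepancy: section 21.3.3 models the task at both T3 and T6, whereas sections 5.1.2 and 8.1 place it at week 5 (T6) only.
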